### **6.1. Subjects randomized to NO-maintenance therapy: the WATCH group**

The subjects randomized to no-treatment will be followed up very closely:

Subjects will have study visits every 4 weeks for the first four months and then every 6 weeks for a total of 24 months of follow-up from randomization. The first visit after randomization will be Visit 1. Visit 1 will be scheduled as soon as possible after randomization.

Subjects will be called by phone by a study coordinator, nurse or physician between each clinic visit for a review of their clinical history to detect any symptoms or signs suggestive of relapse of vasculitis. Should the patient report a symptom or sign suggestive of relapse, she/he will be seen in clinic within the following week for full evaluation. The phone call will be done about 14 days after the clinic visit for the first four months and about 3 weeks after the clinic visit once the subject is followed every 6 weeks. The phone call will be done within a +/- 5 days window. Subject will be trained on the symptoms to watch for and instructed to call study team if such a symptom occurs, without waiting for study phone call or study visit.

Study visits will take place either in the UNC Kidney and Hypertension Clinic, at the Clinical and Translational Research center (CTR) or in the UNC Hospitals Infusion Clinic. Subjects will be examined by a nephrologist, either their regular nephrologist or a nephrologist who is a member of the study team. Study-specific procedures for each visit are outlined below.

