### 6.3.2. Treatment group

**Visit 1/ (= Week 0):** Subjects assigned to treatment groups will receive 500 mg IV rituximab (or start azathioprine or mycophenolate mofetil).

The subject will have a physical exam including BVAS and CDA assessments. We will collect information on concomitant medications and AEs. The subject will be asked to complete a quality of life questionnaire. We will collect 24 ml of blood for research purposes when the subject has blood drawn for routine labs. Women of child-bearing potential will undergo a urine pregnancy test as per indicated clinical care. We will enter the results of routine labs as well as results from B cell analysis in our study database.

**Visits 2 to 13** The subject will have a routine clinical evaluation and a BVAS assessment. We will collect information on adverse events, concomitant medications, and medication compliance. Women of child-bearing potential will undergo a urine pregnancy test as per indicated clinical care. We will enter the results of routine labs in our study database.

Subjects in this treatment groups will receive 500 mg IV rituximab at week 22, week 46, week 70 and week 94 with a +/- 1 week window (or continue azathioprine or mycophenolate mofetil). At those visits, prior to infusion, subjects will have 24 ml of blood drawn for research purposes, including analysis of B cell counts.

The visits will be between every 8 weeks to every 12 weeks, based upon the investigator assessment of how closely an individual subject needs to be followed while on maintenance therapy. The means that the subjects could have between 9 visits (if seen every 12 weeks) and 13 visits (if seen every 8 weeks) until the end of the study.

At week 106, all subjects will undergo a CDA assessment by the nephrologist.

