Time to first positive ANCA test (among those negative at randomization) – The percent who develop a positive ANCA test, and timing to a positive ANCA test will be summarized, with plots of time to this event using Kaplan-Meier curves generated. No statistical analyses for comparisons will be done, but trends and estimates by regimen and by cohort will be used to inform a larger study.

Frequency (number) and severity (by BVAS) of relapse – Among those who relapse, we will evaluate which organs are impacted by disease relapse (using BVAS subsections) and the severity of the relapse

(summarized by the BVAS score). This will be done by regimen and by cohort. Zero in any organ sub-section shows no disease activity in that organ. The total score range for a BVAS is 0 to 64. No statistical analyses are planned, but this will provide information for potential patterns of relapse in specific organs as well as information on the severity of relapses by group.

Occurrence of any infection – all infections will be counted and described by regimen and by cohort.

Frequency/severity/etiology of infections – recurrent infections, severity of infections, with those requiring hospitalization and/or intravenous antibiotics deemed as serious—with etiology of each infection listed. Etiologies will be listed as reported and may include a combination of location (urinary tract, upper respiratory, lung) and type of pathogen (bacterial, viral, fungal or parasitic). All infection metrics (recurrent, severity and type) be described and tallied within each regimen and cohort, but no statistical comparisons will be done. This information is necessary to understand the expected infectious adverse events that can be expected in a larger study.

Frequency and severity of any adverse advent (AEs and SAEs) – These will be catalogued as above for infections – including type of event, relation to therapy/discontinuation of therapy, and outcome of adverse event.

Time to B-cell normalization (that is, % IL-10 Secreting > 45% or % CD5+ B Cells Response > 43%) – the number who normalize will be evaluated; time to normalization will be observed in Kaplan-Meier plots by each regimen and cohort, but no statistical tests will be done to compare groups. These measures will guide the optimal times for follow-up and monitoring in a larger study.

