## Grading the Severity of Adverse Events (Common Terminology Criteria for Adverse Events v.4.0[CTCAE])

### Grades

Grade refers to the severity of the AE. The CTCAE displays Grades 1 through 5 with unique clinical descriptions of severity for each AE based on this general guideline:

- **Grade 1:** Mild; asymptomatic or mild symptoms; clinical or diagnostic observations only; intervention not indicated.
- **Grade 2:** Moderate; minimal, local or noninvasive intervention indicated; limiting age-appropriate instrumental activities of daily living\*. An infection requiring oral antibiotics and resulting in interruption of school or work ≤1 day, is considered a Grade 2 infection.
- **Grade 3:** Severe or medically significant but not immediately life-threatening; hospitalization or prolongation of hospitalization indicated; disabling; limiting self-care activities of daily living\*\*. An infection requiring hospitalization or IV antibiotics or resulting in interruption of school or work > 1 day will be considered a Grade 3 infection
- **Grade 4:** Life-threatening consequences; urgent intervention indicated.
- **Grade 5:** Death related to AE.

\*Instrumental activities of daily living refer to preparing meals, shopping for groceries or clothes, using the telephone, managing money, etc.

\*\*Self-care activities of daily living refer to bathing, dressing and undressing, feeding self, using the toilet, taking medications, and not bedridden.

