## **8.2 Recording of Adverse Events**

At each contact with the subject, the investigator will seek information on adverse events by specific questioning and, as appropriate, by examination. Information on all adverse events will be recorded immediately in the source document, and also in the appropriate adverse event module of the case report form (CRF). All clearly related signs, symptoms, and abnormal diagnostic procedure results will be recorded in the source document, though grouped under one diagnosis.

All adverse events occurring during the study period will be recorded. The clinical course of each event will be followed until resolution, stabilization, or until it has been determined that the study treatment or participation is not the cause. Serious adverse events that are still ongoing at the end of the study period will be followed up to determine the final outcome. Any serious adverse event that occurs after the study period and is considered to be possibly related to the study treatment or study participation will be recorded and reported immediately.

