## APPENDIX C: Script for patient scheduled monitoring calls

Days 15, 30, 45, etc.

"Hello,

This call is to check on how you are feeling and assess whether your vasculitis remains inactive

I will ask you a few questions about symptoms you may feel that could suggest the vasculitis is active or that you may have an infection. In answering, please think about the period of time since your last visit with Dr xxx. If you have any of these symptoms, please also tell me if this is new (in the last 2 weeks, or older) and how severe it is (mild, moderate or severe)"

- 1- Fever
- 2- Ear pain or change in hearing
- 3- Red or painful eyes
- 4- Bleeding from the nose, or sinus pain
- 5- Hoarseness, "air hunger", difficulty taking a deep breath
- 6- Cough or shortness of breath
  - a. If cough, does anything come out? What color? Any blood in the sputum?
  - b. If shortness of breath: is it with exertion (with walking, doing house chores or going up stairs for example), or even at rest? Is it worse at night? Do you feel that you get short of breath more easily than before?
- 7- Chest pain.
  - a. How often, is it on exertion or even at rest? How long does it last? Does it change with position?
- 8- Any nausea or vomiting? How many times did you vomit? Was there any blood in it? When was the last time you vomited? Are you able to eat and keep your food down?
- 9- Any abdominal (belly) pain or diarrhea? Constipation?
  - a. If diarrhea: are the stool soft, black and smelly? Is there any blood in the stool?
- 10- Any joint pain? Are the painful joints red, hot or swollen? How long do they last?
- 11- Any rash? If yes, where is it? Is it on both sides of the body or only one side?
  - a. Is it painful?
  - b. Any open sores
- 12- Any unusual headaches? Is it severe (cannot function)? Is it unusual for you?
- 13- Any new numbness, tingling or weakness in any limb (arms, legs, fingers, toes)?

14- Is there anything else you are concerned about that I did not ask you about?

If any of the above are answered positively:

“Have you called your doctor or the study doctor about this?”

- If yes: “what did the doctor tell you it was?
  - Did she/he prescribe any new medication? Any other change in medication?
  - Do you feel better since?”
- If no: I will relay this to the study doctor and he/she will get back with you and/or see you in clinic in the next 2-3 days.

If none of the questions are answered positively:

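### Mild, self-limited infections and adverse events are likely to be under-counted on maintenance relative to WATCH, because WATCH has more contacts and section 7.2 tallies infections by regimen without allowing for this

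*Combined protocol and SAP*

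**What the plan says.** - **WATCH visits (section 6.1).** "Subjects will have study visits every 4 weeks for the first four months and then every 6 weeks". The schedule table lists 20 visits, from week 0 to week 106.
- **WATCH calls (section 6.1).** There is a call between clinic visits: "The phone call will be done about 14 days after the clinic visit for the first four months and about 3 weeks after" once visits are six-weekly. The Appendix C script asks about "symptoms you may feel that could suggest the vasculitis is active or that you may have an infection"; its items include fever, cough, sinus pain and diarrhoea.
- **Maintenance visits (section 6.3.2).** "The visits will be between every 8 weeks to every 12 weeks, based upon the investigator assessment". The section gives a total of 9 to 13 visits. No symptom calls are scheduled. Under section 6.2 a remote visit replaces a clinic visit that is missing from the 8-to-12-week window; it does not shorten the interval.
- **Elicitation (section 8.2).** "At each contact with the subject, the investigator will seek information on adverse events by specific questioning".
- **Analysis (section 7.2).** All infections are counted by regimen and cohort, and adverse events are catalogued in the same way: "All infection metrics (recurrent, severity and type) be described and tallied within each regimen and cohort". Infections needing hospitalisation or intravenous antibiotics are classed as serious. Aim 1 compares the two randomised groups of Cohort 1 on the outcome variables, and Aim 5 takes estimates forward to a future trial.
- **Partial safeguards.** The missing-data paragraph of 7.2 reports infection counts with and without those known only from the patient, and foresees obtaining outside records. Section 5.5 logs every medication at each visit with start date, end date and indication.

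**The concern.** Questioning about adverse events happens at contacts, and the number of contacts differs by arm by design. A short infection that left no record and is forgotten before the next contact is never counted, and maintenance subjects wait longer for that contact. A raw tally by regimen then mixes the true infection rate with the frequency of asking.

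The frequency and severity of infections is a secondary endpoint (section 3.3). Avoiding the complications of immunosuppression, infections above all, is a large part of the case for omitting maintenance (sections 1 and 11). The expected bias runs against that benefit: infections missed on maintenance make the untreated arm look relatively worse. Since no test is planned, the estimate itself is what passes to the next trial.

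**Working it through.** **1. The plan's own visit counts.** For maintenance, visits = 1 + span/interval. A 96-week span gives 1 + 96/12 = 9 and 1 + 96/8 = 13, which matches section 6.3.2. For WATCH, weeks 0, 4, 8, 12 and 16 make 5 visits, and weeks 22 to 106 in steps of 6 make 15, so 20 in all, as in the schedule table. (Section 6.3.1 also says that the change from four-weekly to six-weekly visits comes after week 64. This conflicts with section 6.1 and the table; the count here follows the listed weeks.)

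**2. Contacts after baseline.** WATCH has 20 − 1 = 19 visits and 19 calls between visits, together 38. Maintenance has 9 − 1 = 8 to 13 − 1 = 12.
- Visits only: 19/12 = 1.6 to 19/8 = 2.4.
- Visits and calls: 38/12 = 3.2 to 38/8 = 4.8.
- If the four later infusions were contacts additional to these visits, maintenance would have 12 to 16. The ratios would then be 38/16 = 2.4 to 38/12 = 3.2 with calls, and 19/16 = 1.2 to 19/12 = 1.6 with visits only.

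**3. Do the calls count?** Section 8.2 covers each contact, and the Appendix C script mentions infection. Yet the call row of the WATCH schedule table marks only the script and concomitant medications and leaves the Adverse Events column blank. The documents do not settle this, so both versions are carried forward.

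**4. What a longer interval could lose.** Longer gaps lose events only if recall fades. The documents give no recall figure, so the following is an assumption. Let the chance of reporting a self-limited infection halve every h weeks, and let infections fall evenly over a contact interval of T weeks. The share captured is (1 − exp(−kT))/(kT), with k = ln 2/h.

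| h (weeks) | T = 3 (WATCH with calls) | T = 6 (WATCH visits only) | T = 8 (maintenance) | T = 12 (maintenance) |
|---|---|---|---|---|
| 8 | 0.881 | 0.780 | 0.721 | 0.622 |
| 13 | 0.924 | 0.856 | 0.814 | 0.739 |
| 26 | 0.961 | 0.924 | 0.901 | 0.856 |

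Maintenance/WATCH capture ratios:

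| h (weeks) | With calls, 8-weekly | With calls, 12-weekly | Visits only, 8-weekly | Visits only, 12-weekly |
|---|---|---|---|---|
| 8 | 0.82 | 0.71 | 0.92 | 0.80 |
| 13 | 0.88 | 0.80 | 0.95 | 0.86 |
| 26 | 0.94 | 0.89 | 0.97 | 0.93 |

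The relative loss exceeds 10% in five of six cases with calls and in two of six with visits only. WATCH gaps are shorter before week 16 (2 weeks with calls, 4 without); these are left out for simplicity, and including them would lower the ratios slightly.

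**5. What this does to an estimate.** At a capture ratio of 0.80, a true 1.25-fold excess of such infections on maintenance would be observed as 1.25 × 0.80 = 1.00, that is, no difference.

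**6. A passage that may pull the other way.** Section 8.1 ends adverse-event reporting 30 days after the last study treatment. WATCH subjects receive none, so their period is undefined. Read literally, the rule could under-count WATCH, although the schedule table marks adverse-event collection at all WATCH visits to week 106.

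**The case against.** **The tallies are descriptive and the safeguards are substantial.** No comparison is tested, with about 15 subjects per randomised arm. Serious infections are already separated, outside records are sought, and medications are logged in both arms. Each visit can ask about the whole time since the last, so a longer interval does not in itself lose events. This stands as a limit on size: what remains exposed is mainly mild infection without a record, and the model in the working ignores charts and logs. It does not remove the point. Outside records help only once the study team knows of the event, and separating patient-only reports cannot restore an infection that nobody mentioned.

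**The size rests on assumption.** This is correct. The half-lives come from no document, and the finding that most cases lose more than 10% depends on the calls eliciting events.

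**The toxicity stopping rule.** A reader might infer that the section 8.4 toxicity criterion is also distorted, because section 8.1 lets time off alone set the grade: "resulting in interruption of school or work > 1 day will be considered a Grade 3 infection". The documents do not support that step. The criterion counts Grade 3 events that are also serious. An infection that reaches Grade 3 only through days off work is not serious for that reason under section 8.1, nor under the infection rule in 7.2. The events that do count mostly leave hospital records, so under-counting there is possible but not shown.

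**Conclusion.** The point holds for mild, self-limited infections and adverse events. Contact after baseline is 1.6 to 2.4 times as frequent in WATCH on visits alone, and 3.2 to 4.8 times if the calls elicit events. Section 7.2 does not allow for this. The likely result is under-counting on maintenance relative to WATCH, with illustrative capture ratios of 0.80 to 0.97 (visits only) and 0.71 to 0.94 (with calls).

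The contact counts follow from the schedules. The capture ratios rest on assumed half-lives of 8 to 26 weeks and take no credit for records and medication logs, which would bring them nearer to 1. The undefined reporting period for WATCH makes the direction likely rather than certain. A reader might also infer that the trial will hide or reverse an infection benefit of omitting maintenance. The documents do not show that; they show an avoidable bias in a descriptive estimate meant for planning. The remedy is cheap and worth making.

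**What to change.** 1. **Section 7.2, lead comparison.** For Cohort 1, A against B, lead with infections needing hospitalisation or intravenous antibiotics, which 7.2 already classes as serious. Supplement this with infections that have a prescribed anti-infective in the concomitant-medication log, using the recorded indication to leave out prophylaxis.
2. **All-infection tally.** Report it as secondary, with a caveat that contact was unequal.
3. **Mode of detection.** Add one field to the adverse-event form for how each infection was first detected: call, scheduled visit, patient-initiated contact or outside record. Give the tally with and without infections detected only at calls.
4. **Reconcile the text.** State whether adverse events are collected at WATCH calls (schedule table against section 8.2 and Appendix C), and define the reporting period for subjects who receive no study treatment (section 8.1).

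A single identical question at the visits that both arms share (weeks 22, 46, 70 and 94) is tempting as the basis for the all-infection count, but it is not recommended. It implies about 24 weeks of recall, and the same formula then captures only 42%, 56% and 74% at half-lives of 8, 13 and 26 weeks.

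**Cost.** Wording changes and one form field; the WATCH calls stay as they are. The lead comparison will have fewer events and will omit mild untreated infections. Anti-infective prescribing is not fully independent of contact either, because a positive WATCH call leads to physician follow-up.

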B cell subsets will be measured in the UNC Hospitals clinical lab as per our standard of care after treatment with rituximab. We will measure % of CD19+ by flow cytometry. A sample will be obtained for research analysis with each clinical sample to determine the %CD19+CD5+ B cells. For study inclusion, we will require a minimum threshold of 50 CD5+CD19+ **total detectable** events to assess this percentage. In the WATCH group, the first sample will be obtained at the time of enrollment, 6, and 12 weeks later and then at every visit subsequently until CD19+ B cell are  $\geq 1\%$ . In the maintenance therapy group, B cell subsets will be measured at the time of enrollment, and prior to each Rituximab infusion until Month 24. For subjects on maintenance therapy with azathioprine or mycophenolate mofetil, B-cell subsets will be measured at enrollment, week 22, week 46, week 70 and week 94.. Detailed B cell phenotyping and measure of IL-10 production will be performed at the same time as CD5+ analysis.

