## 5 Study Drug

### 5.1 Description

**See section 1.2**

### 5.2 Treatment Regimen

**See section 1.4**

### 5.3 Method for Assigning Subjects to Treatment Groups

All subjects whose CD5+ B cells account for less than 43% of total CD19 B cells will be assigned to maintenance therapy. Those subjects with CD5+CD19+ B cells  $\geq 43\%$  will be randomized as follows:

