Maintenance therapy with rituximab (Rituxan) is administered at 500 mg IV every 6 months. The visit numbers when the infusion will happen are indicative. Infusion will be scheduled at week 0, week 22, week 46, week 70 and week 94 +/-1 week. Patients who are allergic or intolerant to rituximab or cannot access rituximab will receive maintenance therapy with azathioprine (Imuran) 1.5-2 mg/kg/day or mycophenolate mofetil (CellCept) 1000 mg twice daily. In the maintenance therapy group, B cell subsets will be measured prior to Rituximab infusion until Month 24. For subjects on maintenance therapy with azathioprine or mycophenolate mofetil, B-cell subsets will be measured at week 22, week 46, week 70 and week 94

Xi: Quality of Life questionnaire is administered at infusion visit.

- The last study visit will take place when the 2 years post-randomization timepoint is reached.

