### 7.1 Sample Size Determination

Based on our ANCA cohort registry, we estimate being able to enroll 40 eligible patients over a period of 24 months. Based on our previous studies, we estimate that ~31 patients (78%) will recover  $\geq 43\%$  CD5+ B cells after induction therapy and will be randomized to maintenance vs NO maintenance immunosuppressive therapy arm. We anticipate 9 patients (22%) will fall in the “low” CD5+ B cell category and will receive maintenance therapy with rituximab, azathioprine or mycophenolate mofetil.

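### In Cohort 2, one unconfirmed CD5+ reading above the 43% entry line, or an IL-10 reading above 45% that may predate entry, counts as B-cell normalization, so chance crossings can inflate and advance the curve

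*Combined protocol and SAP*

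**What the plan says.** - **Entry.** Section 5.3: "All subjects whose CD5+ B cells account for less than 43% of total CD19 B cells will be assigned to maintenance therapy". These patients form Cohort 2 in Section 7.2. Section 7.1 expects them to be the smaller group: "we estimate that ~31 patients (78%) will recover" to at least 43%, and "We anticipate 9 patients (22%) will fall in the" low category.
- **Event.** Section 7.2 analyses "Time to B-cell normalization (that is, % IL-10 Secreting > 45% or % CD5+ B Cells Response > 43" percent, by regimen and cohort, without tests. It says these measures will inform when to follow up and monitor patients in a larger study. No minimum rise, repeat sample or persistence is required. The missing-data paragraph of 7.2 lets the next available value set the time to normalization, so one value suffices.
- **Looks.** Section 3.1, for the maintenance group: "B cell subsets will be measured at the time of enrollment, and prior to each Rituximab infusion until Month 24". The notes to the visit schedules in Section 6 add: "Infusion will be scheduled at week 0, week 22, week 46, week 70 and week 94 +/-1 week". Section 3.1 gives patients on azathioprine or mycophenolate the same later weeks.
- **Assay.** Section 3.1: "For study inclusion, we will require a minimum threshold of 50 CD5+CD19"+ events. It also says CD5+ B cells can be quantified reliably once CD19+ cells are at least 1% of lymphocytes. No repeatability figure appears.
- **Wording of the endpoint.** Section 2 and Section 7.2 describe time to crossing a threshold. Item 4 of Section 3.3 describes time to relapse after crossing.

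**The concern.** The line that puts a patient into Cohort 2 is also the line that ends the wait for normalization. A patient whose stable level is 41% can read 42% at enrollment and 44% at week 46 and be counted as recovered. Two ordinary mechanisms push this way. Patients selected on one low reading tend to read higher next time, and each further look adds another chance to cross.

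Two gaps add to it. The week 0 sample of a rituximab patient is drawn before the first dose, and nothing stops a reading above 43% there from counting as the event. The IL-10 criterion is joined by *or* and plays no part in entry, so a Cohort 2 patient already above 45% is normalized at time zero. Section 7.2 does restrict time to positive ANCA to patients negative at randomization; no such restriction is written here.

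At stake is a planning input. A curve that is too high and too early would mislead the choice of monitoring times for the next trial. With about 9 patients, two or three chance events change its shape. The primary outcome is not touched.

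**Working it through.** **The plan's own figure.** 40 x 0.78 = 31.2 and 40 x 0.22 = 8.8, which match the stated 31 and 9.

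**Inputs from the documents.** 22% of first readings below 43%; four looks after week 0 (weeks 22, 46, 70, 94), or five if week 0 counts; one reading above 43% is enough.

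**Inputs assumed.** Between-patient SD B = 8, 12 or 15 points; within-patient SD e = 1 to 6.5 points; normal, independent errors; no true change; every look evaluable.

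**One reference value for e.** If a 43% reading rests on exactly 50 CD5+ events, it rests on 50/0.43 = 116 B cells. The counting SD is 100 x sqrt(0.43 x 0.57/116) = 4.6 points. This is counting error at the inclusion minimum, not a typical value taken from the documents.

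**Model.** Let T be the patient's true level, Normal with SD B, its mean set so that 22% of first readings fall below 43. Let L = Phi((43 - T)/e) be the chance that a reading is low, and H = 1 - L. Averaging over T (E):

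- at least one of k later readings above 43, given a low first reading: 1 - E[L^(k+1)] / E[L]
- two consecutive high readings among four: 1 - E[L x (L^4 + 4HL^3 + 3H^2L^2)] / E[L]

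**Single-reading rule, four looks, no true change (percent, to within about a point):**

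| B | e = 1 | e = 2.2 | e = 3 | e = 4.6 | e = 6.5 |
|---|---|---|---|---|---|
| 8 | 19 | 39 | 50 | 67 | 80 |
| 12 | 13 | 27 | 35 | 51 | 65 |
| 15 | 10 | 22 | 29 | 42 | 56 |

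Of 9 patients that is 0.9 (10%) to 7.2 (80%). In reliability terms, B^2/(B^2 + e^2) runs from 64/106.25 = 0.60 to 225/226 = 0.996.

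**One evaluable look.** 5% (B = 15, e = 1) to 48% (B = 8, e = 6.5); 27% at B = 12, e = 4.6.

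**Counting week 0 as a fifth look.** 51% becomes 54% at B = 12, e = 4.6.

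**Two consecutive readings above 43, four looks.** 4% to 48% over the same grid; 25% at B = 12, e = 4.6. Confirmation cuts chance crossings by 40% or more but does not remove them.

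**A stricter rule, at B = 12, e = 4.6.** Suppose both the enrollment and week 0 readings must be below 43, with confirmation and a minimum rise over their mean of 2 SDs of change: 2 x 4.6 x sqrt(2) = 13.0 points, or 2 x 4.6 x sqrt(1.5) = 11.3 points if the SD allows for averaging two baselines. False crossings fall below 3%. However, about 27% of Cohort 2 drops out on the second baseline. Simulating a true, sustained 10-point rise in the same model, the rule detects only about 34% to 70% of the remaining patients whose true level crosses 43, depending on which minimum rise is used and whether one or both readings must meet it. Simple confirmation detects about 90% of true 10-point crossings.

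**The case against.** The strongest reply is that 43% is the trial's operating line, applied to one reading at entry, so first crossing of that line is a fair descriptive quantity for planning visits. That stands, and it is why the single-reading curve should stay. It does not explain why a pre-dose sample or an IL-10 value already high at entry may count as recovery.

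The second reply concerns size, and most of it stands. The documents give neither SD. The 4.6-point figure puts every reading at an event minimum stated only for inclusion; with a within-patient SD near 1 point the four-look share is 10% to 19%. Four evaluable looks are also doubtful. Most of Cohort 2 is due rituximab about every six months, and CD5+ is reliably measured only when CD19+ is at least 1%. A B-cell population depleted and regrown between samples need not keep a fixed CD5+ share. In the other direction, no event minimum is stated for follow-up samples, so some readings could be noisier than 4.6 points.

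Third, the curve is imprecise under any definition: 4 of 9 has an exact 95% interval of 14% to 79%. That limits the importance of the point but does not make a biased definition preferable.

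**Conclusion.** The point holds as a gap in the endpoint definition. Entry and event share one line, a single reading decides, and neither a week 0 crossing nor an IL-10 value above 45% at entry is ruled out as an event. Each of these pushes the Cohort 2 curve up and to the left.

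The size is a range under assumptions: about 10% to 80% over four evaluable looks and about 5% to 48% on one, given the plan's 22% share, the SDs above, independent normal errors and no true change. These figures cover the CD5+ criterion alone; the IL-10 criterion can only add to them.

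A reader might infer that noise will normalize a fifth to four fifths of Cohort 2, or that the curve would mostly describe assay error. The documents do not support either. They contain no reliability figure, a precise assay falls below that range, and the number of evaluable samples after rituximab is unknown.

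The point is minor. It concerns a descriptive secondary endpoint in about 9 patients, with no tests planned and no bearing on time to first relapse.

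**What to change.** In Section 7.2:

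1. Report the CD5+ and IL-10 criteria as separate outcomes, each only among patients not above that threshold at enrollment. For CD5+ this in effect leaves Cohort 2, since Cohort 1 enters at 43% or more.
2. Treat the week 0 pre-dose sample as part of baseline. A reading above the line there is tabulated and is not an event.
3. For CD5+, keep the single-reading curve and add a confirmed-crossing analysis beside it: above 43% at two consecutive evaluable samples, dated at the first. State the number of evaluable samples per patient.
4. Report the observed enrollment-to-Visit 1 variability for context. Standard-of-care visits while B cells recover may fall between the two samples, so the difference can include real change and should not define the event.
5. Do not make the two-baseline, 2-SD minimum-rise rule the main definition; it loses patients and misses many true rises.
6. Reconcile item 4 of Section 3.3 with Section 2 and Section 7.2, so that one endpoint is described throughout.

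The cost is wording only, with samples already scheduled. A first crossing at week 94 cannot be confirmed, fewer patients will count as normalized, and in the model some chance crossings remain after confirmation.
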